4.2 Preliminary Data and Interim Analysis

No interim analysis is planned for this study.

5. TREATMENT DESCRIPTIONS

LOXO-292 will be supplied as 80 mg capsules.

Repaglinide will be supplied as 0.5 mg tablets.

Glucose will be provided as 4 g chewable tablets.

Each dose of LOXO-292 and repaglinide will be administered orally with 240 mL of room temperature water. When LOXO-292 and repaglinide are administered concurrently, only 240 mL of room temperature water will be administered for both drugs. The dose of repaglinide on Day 1 of Period 1 and the coadministered morning doses of LOXO-292 and repaglinide on Day 10 of Period 2 will be preceded by an overnight fast of at least 10 hours. All other doses will be preceded by a 2-hour fast and followed by a 1 hour postdose fast.

On Day 1 of Period 1, immediately following administration of repaglinide, subjects will be provided with 12 g of glucose (3 x 4 g chewable tablets). On Day 10 of Period 2, immediately following administration of repaglinide and at approximately 1 hour after administration of repaglinide, subjects will be provided with 16 g of glucose (4 x 4 g chewable tablets). An additional 100 mL of room temperature water may be taken if required.

Subjects will be instructed not to crush, split, or chew LOXO-292 capsules or repaglinide tablets, and will be instructed to chew the glucose tablets.

All Subjects (n = 16)

Table 5.1 Treatment Description

Treatment	Short Description (text, tables headers, figures, listings, SAS output)	Description
A (Period 1)	0.5 mg repaglinide	A single dose of 0.5 mg repaglinide administered at Hour 0 on Day 1
B* (Period 2)	0.5 mg repaglinide + MD 160 mg LOXO-292	Multiple doses of 160 mg LOXO-292 (2 x 80 mg capsules) administered BID, approximately every 12 hours, for 10 consecutive days with 0.5 mg repaglinide coadministered on the morning of Day 10
B1	MD 160 mg LOXO-292 Alone	Multiple doses of 160 mg LOXO-292 BID from Day 1 to Day 9

B2	0.5 mg repaglinide + MD 160 mg LOXO-292	Multiple doses of 160 mg LOXO-292 BID on Day 10 with a single dose of 0.5 mg repaglinide coadministered on the morning of Day 10
----	--	--

* For AEs, Treatment B will be divided into two segments as B1 and B2.
MD = multiple dose

6. PHARMACOKINETIC ANALYSIS

6.1 Measurements and Collection Schedule

Blood samples for PK assessment of repaglinide will be taken at the following time points on Day CCI [REDACTED]

Blood samples for PK assessment of LOXO-292 will be taken at the following time points after the morning dose on Days CCI [REDACTED]

[REDACTED] . Trough samples will be taken following the CCI [REDACTED]

All concentration data will be included in the calculation of the individual PK parameters, the individual concentration-time plots (based on actual sample times), and in the mean concentration-time plots (based on nominal sample times). However, if there are any significant deviations from nominal sample times, some concentration data may be excluded from mean concentration-time plots and/or additional concentration-time plots of the mean data may be provided. All deviations and excluded data will be provided and discussed in the CSR.

6.2 Bioanalytical Method

6.2.1 Repaglinide

Plasma concentrations of repaglinide will be determined using a liquid chromatography-tandem mass spectrometry (LC-MS/MS) method validated with respect to accuracy, precision, linearity, sensitivity, and specificity at Alturas Analytics, Inc. (Moscow, Idaho, USA). The analytical range (lower limit of quantitation [LLOQ] – upper limit of quantitation [ULOQ]) for repaglinide in plasma is 0.02 – 20 ng/mL.

6.2.2 LOXO-292

Plasma concentrations of LOXO-292 will be determined using LC-MS/MS method validated with respect to accuracy, precision, linearity, sensitivity, and specificity at

Alturas Analytics, Inc. (Moscow, Idaho, USA). The analytical range (LLOQ – ULOQ) for LOXO-292 in plasma is 1 – 1000 ng/mL. Samples that contain concentrations greater than 1000 ng/mL may be diluted up to 51-fold, if necessary, to be within the quantification range.

6.3 Investigational Product and PK Analyte Information

6.3.1 Repaglinide

Repaglinide was supplied as repaglinide 0.5 mg tablets, each 0.5 mg contained 0.5 mg of repaglinide (freebase).

6.3.2 LOXO-292

LOXO-292 has a molecular weight of approximately 500 g/mol. LOXO-292 was supplied as a simple blend with excipients containing 80 mg of drug substance (freebase) in a hard gelatin capsule.

6.4 Pharmacokinetic Concentrations

Plasma concentrations of repaglinide and LOXO-292 as determined at the collection times and per the bioanalytical methods described in Section 6.1 and Section 6.2, respectively, will be used for the calculation of the plasma repaglinide and LOXO 292 PK parameters.

6.5 Noncompartmental Pharmacokinetic Analysis and Parameter Calculation for Repaglinide and LOXO-292

The appropriate noncompartmental PK parameters will be calculated from the plasma repaglinide and LOXO-292 concentration-time data using Phoenix® WinNonlin® Version 7.0 or higher. Actual sample collection times will be used in the calculations of the PK parameters. The calculation of the actual time for repaglinide will be in respect to the dose administration time of repaglinide on Day 1 of Period 1 and Day 10 of Period 2. The calculation of the actual time for LOXO-292 will be in respect to the administration time of the morning LOXO-292 dose on Days 1 and 10 in Period 2. All PK parameters included in the protocol are listed in Tables 6.1, 6.2, and 6.3 below, and are defined as appropriate for study design.

Table 6.1. Noncompartmental Pharmacokinetic Parameters to be Calculated for Repaglinide

Label to be Used in the Text, Tables and Figures	Definition	Method of Determination
AUC0-t	Area under the concentration-time curve from time 0 to the time of the last observed non-zero concentration	Calculated using the Linear Trapezoidal with Linear Interpolation Method
AUC0-inf	Area under the concentration-time curve from time 0 extrapolated to infinity	Calculated as AUC0-t + (Clast/Kel) where Clast is the last observed/measured concentration
AUC%extrap	Percent of AUC0-inf extrapolated	Calculated as (1- AUC0-t/AUC0-inf)*100
Cmax	Maximum observed concentration	Taken directly from bioanalytical data
Tmax	The time to reach Cmax. If the maximum value occurs at more than one time point, Tmax is defined as the first time point with this value	Taken from clinical database as the difference in the time of administration and the time of the blood draw which is associated with the Cmax.
Kel	Apparent terminal elimination rate constant; represents the fraction of drug eliminated per unit time	Calculated as the negative of the slope of a linear regression of the log(concentration)-time for all concentrations >LLOQ during the terminal elimination phase
t½	Apparent first-order terminal elimination half-life	Calculated as 0.693/Kel
CL/F	Apparent total plasma clearance after oral (extravascular) administration	Calculated as Dose/(AUC0-inf)
Vz/F	The apparent volume of distribution during the terminal elimination phase after extravascular administration	Calculated as Dose/(AUC0-inf x Kel)

Table 6.2. Single-dose Noncompartmental Pharmacokinetic Parameters to be Calculated for LOXO-292 on Day 1

Label to be Used in the Text, Tables and Figures	Definition	Method of Determination
AUC0-12	Area under the concentration-time curve from time 0 to 12 hours	Calculated using the Linear Trapezoidal with Linear Interpolation Method
AUC0-t	Area under the concentration-time curve from time 0 to the time of the last observed non-zero concentration	Calculated using the Linear Trapezoidal with Linear Interpolation Method
Cmax	Maximum observed concentration	Taken directly from bioanalytical data
Tmax	The time to reach Cmax. If the maximum value occurs at more than one time point, Tmax is defined as the first time point with this value	Taken from clinical database as the difference in the time of administration and the time of the blood draw which is associated with the Cmax.

Table 6.3. Multiple-dose Noncompartmental Pharmacokinetic Parameters to be Calculated for LOXO-292 on Day 10

Label to be Used in the Text, Tables and Figures	Definition	Method of Determination
AUCtau	Area under the concentration-time curve during a dosing interval, tau, at steady state Will be calculated after the morning dose, where tau is defined as 12 hours	Calculated using the Linear Trapezoidal with Linear Interpolation Method
Cmax,ss	The maximum observed concentration at steady state, following the morning dose	Taken directly from bioanalytical data
Ctrough*	Concentration observed at the end of a dosing interval Dosing interval is defined as 12 hours following the 2 nd dose on Days 1, 2, 3, 4, 5, 6, 7, 8, and 9 (corresponding to pre-morning dose samples collected on Days 2, 3, 4, 5, 6, 7, 8, 9, and 10)	Taken directly from bioanalytical data at any given time point

Label to be Used in the Text, Tables and Figures	Definition	Method of Determination
Tmax,ss	The time to reach Cmax at steady state, following the morning dose	Taken from clinical database as the difference in the time of administration and the time of the blood draw which is associated with the Cmax.
CL,ss/F	Apparent total body clearance estimated at steady state after oral/extravascular administration	Calculated as Dose/AUC _{tau,ss}

CCI

Pharmacokinetic parameters will not be calculated for subjects with fewer than 3 consecutive postdose time points with quantifiable concentrations. Subjects for whom there are insufficient data to calculate the PK parameters will be included in the concentration tables only and excluded from all statistical analysis.

For the calculation of the PK parameters on Day 1 and Day 10, plasma concentrations below the limit of quantitation (BLQ) prior to the first quantifiable concentration of a PK profile will be set to 0 and plasma concentrations BLQ after the first quantifiable concentration of a PK profile will be treated as missing.

The Kel will be determined using linear regressions composed of least 3 data points. The Kel will not be assigned if 1) the terminal elimination phase is not apparent, 2) if Tmax is one of the 3 last data points, or 3) if the R^2 value is less than 0.75. In cases where the Kel interval is not assigned, the values of $t_{1/2}$, AUC_{0-inf}, AUC%extrap, CL/F, CL,ss/F, and Vz/F, as appropriate, are considered not calculable and will not be reported. Wherever the resulting $t_{1/2}$ is more than half as long as the sampling interval, the Kel values and associated parameters ($t_{1/2}$, AUC_{0-inf}, AUC%extrap, CL/F, CL,ss/F, and Vz/F) may not be presented as judged appropriate and in accordance with Celerion SOPs.

6.6 Data Summarization and Presentation

All repaglinide and LOXO-292 PK concentrations and PK parameters descriptive statistics will be generated using SAS® Version 9.3 or higher.

The plasma concentrations of repaglinide will be listed and summarized by treatment and time point for all subjects in the PK Population. The plasma concentrations of LOXO-292 will be listed and summarized by Study Day and time point for all subjects in the PK Population. Plasma concentrations of repaglinide and LOXO-292 will be presented with the same level of precision as received from the bioanalytical

laboratory. Summary statistics, including sample size (n), arithmetic mean (Mean), standard deviation (SD), coefficient of variation (CV%), standard error of the mean (SEM), minimum, median, and maximum will be calculated for all nominal concentration time points. Excluded subjects will be included in the concentration listings, but will be excluded from the summary statistics and noted as such in the tables. All BLQ values will be presented as “BLQ” in the concentration listings and footnoted accordingly.

Mean and individual concentration-time profiles will be presented on linear and semi-log scales. Linear mean plots will be presented with and without SD.

Plasma repaglinide PK parameters will be listed and summarized by treatment for all subjects in the PK Population. Plasma LOXO-292 PK parameters will be listed and summarized by Study Day for all subjects in the PK Population. PK parameters will be reported to 3 significant figures for individual parameters, with the exception of Tmax and t½, which will be presented with 2 decimal places. Summary statistics (n, Mean, SD, CV%, SEM, minimum, median, maximum, geometric mean [Geom Mean] and geometric CV% [Geom CV%]) will be calculated for plasma repaglinide and LOXO-292 PK parameters. Excluded subjects will be listed in the PK parameter tables, but will be excluded from the summary statistics and noted as such in the tables.

The level of precision for each concentration and PK parameter statistic will be presented as follows:

- minimum/maximum in same precision as in bioanalytical data and parameter output,
- mean/median/Geom Mean in one more level of precision than minimum/maximum,
- SD/SEM in one more level of precision than mean/median/Geom Mean,
- n will be presented as an integer, and
- CV%/ Geom CV% will be presented to the nearest tenth.

6.7 Statistical Analysis of PK

6.7.1 Analysis of Variance of PK Parameters

PK parameters (AUC0-t, AUC0-inf, and Cmax) of repaglinide will be natural log (ln)-transformed and analyzed by an analysis of variance (ANOVA) to evaluate the effects of multiple-dose administration of LOXO-292 on repaglinide (Treatment B Versus Treatment A) using PROC MIXED in SAS®. The ANOVA model will include treatment as a fixed-effect and subject as a random-effect. The Kenward and

Roger adjustment will be used to calculate the denominator degrees of freedom for the fixed-effects (DDFM=KR). Each ANOVA will include calculation of least-squares means (LSMs), the difference between treatment LSMs, the standard error and 90% confidence intervals (CIs) associated with this difference. The ANOVA analysis will be performed using the following SAS® code:

CCI

Ratios of LSMs and associated 90% CIs of ratios will be calculated by exponentiation of the difference between two treatment LSMs and the corresponding CIs from the ANOVA analyses on the ln-transformed repaglinide AUC0-t, AUC0-inf, and Cmax when repaglinide is coadministered with LOXO-292 (Treatment B) versus when administered alone (Treatment A). These ratios and CIs will be expressed as a percentage relative to the reference treatment (Treatment A). Geometric LSMs, GMRs, and 90% CIs will be presented.

[figure not shown]
6.7.2 Steady-State Analysis of LOXO-292

A steady-state analysis will be performed on the ln-transformed Ctrough concentrations for LOXO-292, on Days CCI

using Helmert contrasts. Additional Ctrough concentrations CCI may be used, if warranted, for the steady-state analysis to gather more information on steady-state attainment.

Helmert contrasts are constructed such that each time point is compared to the mean of the subsequent time points. Steady state will be concluded at the time point where no more statistical difference (alpha=5%) can be observed. The contrasts will be:

CCI

CCI

The steady-state analysis will be conducted using PROC MIXED of SAS®. The following SAS® code will be used.

CCI

The variance-covariance matrices &TYPE: UN, CS, CSH, AR(1), VC, ARH(1), ARMA(1,1) will be tried. The one with the smallest AICC will be chosen.

7. SAFETY

No inferential statistics are to be performed for the safety analysis.

All clinical safety and tolerability data will be listed by subject and assessment time points, including rechecks, unscheduled assessments, and early termination (ET), chronologically.

Continuous variables will be summarized using n, mean, SD, minimum, median, and maximum. Frequency counts will be reported for categorical data when appropriate.

The level of precision will be presented as follows: “n” as an integer, minimum/maximum in same precision as in the database, mean/median in one more precision level than minimum/maximum, and SD in one more precision level than mean/median.

Where individual data points are missing because of dropouts or other reasons, the data will be summarized based on reduced denominators.

When change from baseline is calculated, baseline is the last scheduled assessment before dosing at Period 1, including rechecks and unscheduled assessments, whichever is later, unless otherwise specified in the sections below. Rechecks, unscheduled assessments and ET measurements taken after first dosing will not be used in the summarization.

7.1 Subject Discontinuation

Subjects will be summarized by the number of subjects enrolled, completed, and discontinued from the study with discontinuation reasons by treatment and overall. Discontinuation data will be listed by-subject.

7.2 Demographics

Descriptive statistics will be calculated for continuous variables (age, weight, height, and body mass index) for study overall. Weight, height and body mass index are summarized at screening. Age will be derived from the date of birth to the date of first dosing at Period 1. Frequency counts will be provided for categorical variables (race, ethnicity, and sex) for overall. A by-subject listing will also be provided.

7.3 Adverse Events

All AEs occurring during this clinical trial will be coded using the Medical Dictionary for Regulatory Activities (MedDRA®), Version 21.1.

Each AE will be graded, by the clinical site, on the National Institution of Health's Common Terminology Criteria for Adverse Events (CTCAE, version 5.0) 5-point severity scale (Grade 1, 2, 3, 4 and 5). Not all grades are appropriate for all AEs. Therefore, some AEs are listed within the CTCAE with fewer than 5 options for grade selection.

The following clinical descriptions of severity for each AE are based on the following general guideline [[CTCAE Nov2017](#)]:

Table 7.3: Adverse Event Severity Level and Description

Grade	Description
Grade 1	Mild; asymptomatic or mild symptoms; clinical or diagnostic observations only; intervention not indicated.
Grade 2	Moderate; minimal, local or noninvasive intervention indicated; limiting age-appropriate instrumental activities of daily living (ADL)*.

Grade	Description
Grade 3	Severe or medically significant but not immediately life-threatening; hospitalization or prolongation of hospitalization indicated; disabling; limiting self-care ADL**.
Grade 4	Life-threatening consequences; urgent intervention indicated.
Grade 5	Death related to AE.

* Instrumental ADL refer to preparing meals, shopping for groceries or clothes, using the telephone, managing money, etc.
** Self-care ADL refer to bathing, dressing and undressing, feeding self, using the toilet, taking medications and not bedridden.

Similarly, the causal relationship of the study drugs to the AE will be described as Related or Unrelated to study drugs LOXO-292 and/or Repaglinide.

All AEs captured in the database will be listed in by-subject data listings including verbatim term, coded term, treatment group, severity grade, relationship to study drugs, and action; however, only treatment-emergent AEs (TEAEs) will be summarized.

A TEAE is defined as an undesirable event not present prior to medical treatment, or an already present event that worsens either in intensity or frequency following the treatment. Each TEAE will be attributed to a treatment based on Investigator (or designee) judgment as well as on its onset date and time. An AE that occurs during the washout period between treatments will be considered treatment-emergent to the last treatment given. If an AE has a change in severity grade, the original AE will be given a resolution date and time of the time of severity grade increase or decrease and a new AE record will be initiated with the new severity grade, and the new AE record will use the resolved date/time of the previous record as the onset date/time. If an AE decreases in severity grade, the new AE record with less severity will be considered and counted as the same AE event of the previous record with worse severity under the same treatment group and period in the analysis. If the severity grade of an AE remains the same, the AE will be kept open through to resolution.

If the onset time of an AE is missing and the onset date is the same as the treatment dosing date, then the AE will be considered treatment-emergent in both the prior and current treatment. If the onset time of an AE is missing and the onset date does not fall on a dosing date, then the AE will be considered treatment-emergent for the last treatment administered. If the onset date of an AE is missing, then the AE will be considered treatment-emergent and attributed to the first treatment group on the

study, unless the onset date is known to have occurred within or between specific treatment periods. For an AE with multiple changes in severity, a new record with severity less or equal to its maximum severity will not be considered as a new event in the summary tables.

TEAEs will be tabulated by system organ class and preferred term. Summary tables will include the number of subjects reporting the AE and as a percent of the number of subjects dosed by treatment and overall. Treatment B will be divided into two segments as B1 (Multiple doses of 160 mg LOXO-292 BID from Day 1 to Day 9) and B2 (Multiple doses of 160 mg LOXO-292 BID on Day 10 with a single dose of 0.5 mg repaglinide coadministered on the morning of Day 10) (see [Table 5.1](#)). Tables will also be presented by severity grade and relationship to study drugs. If a subject experienced the same TEAE at more than once with different level of severity grade for a given treatment, only the most severe one will be counted. Similarly, if a subject experienced the same TEAE at more than once with different level of drug relationship for a given treatment, only the one most closely related to the study drug will be counted.

Should any serious adverse events (SAEs) occur during the study, the SAEs will be displayed in a table and a narrative included in the Clinical Study Report.

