12.3 Method of Treatment Assignment

Each subject will be assigned a unique identification number upon screening. Subjects who complete the study screening assessments and meet all the eligibility criteria will be assigned a unique identification number at the time of the first dosing, different from the screening number, and will receive the corresponding product.

Subjects will receive each treatment on one occasion in a fixed sequence. The sequence to be used will be AB.

If replacement subjects are used, the replacement subject number will be 100 more than the original (e.g., Subject No. 101 will replace Subject No. 001).

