3. STUDY DESIGN

This is an open label, 2-period, fixed-sequence study.

Sixteen (16), healthy, adult male and female (women of non-childbearing potential only) subjects will be enrolled. Every attempt will be made to enroll at least 3 subjects of each sex.

Screening of subjects will occur within 28 days prior to the first dosing (i.e., repaglinide).

In Period 1, Day 1, a single oral dose of repaglinide will be administered. PK samples for repaglinide will be collected predose and for 16 hours postdose.

In Period 2, oral doses of LOXO-292 will be administered twice daily (BID) for 10 consecutive days (Days 1 to 10). The single dose of repaglinide will be coadministered with the single dose of LOXO-292 on the morning of Day 10. PK sampling for repaglinide will be collected predose and for 16 hours following repaglinide dosing on Day 10. PK sampling in plasma for LOXO-292 will be collected CCI

In both periods, glucose will be administered immediately following repaglinide dosing on Day 1 of Period 1 and Day 10 of Period 2 and additionally, at approximately 1 hour postdose on Day 10 of Period 2.

There will be a washout period of 24 hours between the repaglinide dose in Period 1 and the first LOXO-292 dose in Period 2.

Safety and tolerability will be assessed through End of Treatment (EOT) or early termination (ET) by monitoring AEs, performing physical examinations, glucose monitoring, and clinical laboratory tests, measuring vital signs, and recording ECGs.

Subjects will be permitted to be replaced at the discretion of the Sponsor.

Subjects will be housed through EOT or ET beginning in Period 1, Day -1, at the time indicated by the clinical research unit (CRU), until after completion of study procedures in Period 2, Day 11 (EOT) or ET study procedures.

The CRU will contact all subjects who received at least one dose of study drug (including subjects who terminated the study early [ET]) at the End of Study (EOS) by a follow up (FU) phone call. The EOS/FU phone call will be performed 7 ± 2 days after the EOT visit or ET visit to determine if any SAE or study drug related AE has occurred since the EOT or ET visit.

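### An adverse event whose onset cannot be placed in any period is counted under repaglinide alone by default, which can understate the LOXO-292 columns

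*SAP*

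**What the plan says.** SAP Section 7.3 gives a general attribution rule and then several rules for particular cases.

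- **General rule:** "Each TEAE will be attributed to a treatment based on Investigator (or designee) judgment as well as on its onset date and time".
- **Onset in the washout between treatments:** the event goes to the treatment most recently given.
- **Onset time missing, onset on a dosing date:** "then the AE will be considered treatment-emergent in both the prior and current treatment".
- **Onset time missing, any other date:** if "the onset date does not fall on a dosing date, then the AE will be considered treatment-emergent for the last treatment administered".
- **Onset date missing:** "If the onset date of an AE is missing, then the AE will be considered treatment-emergent and attributed to the first treatment group", with the exception "unless the onset date is known to have occurred within or between specific treatment periods".

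Protocol Section 12.3 fixes the order for all subjects: "The sequence to be used will be AB". SAP Table 5.1 defines Treatment A as "A single dose of 0.5 mg repaglinide administered at Hour 0 on Day 1". For adverse events it splits Treatment B into B1 (LOXO-292 on Days 1 to 9) and B2 (Day 10, with repaglinide). The treatment-emergent event tables show A, B1, B2 and Overall.

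**The concern.** In a design with randomised sequences, sending undated events to the first treatment would spread them over the treatments. Here the sequence is fixed, so the residual default always lands on the one segment without LOXO-292. Any error it makes goes one way: the Treatment A count rises and the B1 or B2 count falls.

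Secondary objective 2 is the safety and tolerability of LOXO-292 with and without repaglinide, which is read from columns B2 and B1. SAP Section 7 plans no inferential safety analysis, so these counts are the analysis.

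There is also a matter of presentation. Table 14.3.1.2 crosses treatment with relationship to LOXO-292. Read literally, an undated event judged related to LOXO-292 could appear in the Treatment A row, before any LOXO-292 had been given.

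**Working it through.** The documents give no figure for this rule, so there is none to reproduce. The check compares the rules and then sizes the default.

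**1. Direction of each placement rule (SAP 7.3)**

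| Case | Counted under | Most recent treatment kept? |
|---|---|---|
| Onset in washout | last treatment given | yes |
| Time missing, dosing date | prior and current | yes |
| Time missing, other date | last treatment | yes |
| Date missing, period known | exempt from the default | not applicable |
| Date missing, period unknown | first treatment only, always A | no |

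Only the last row assigns the event solely to the earliest treatment.

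**2. Length of each window**

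- A: 1 day. SAP Section 3: "There will be a washout period of 24 hours between the repaglinide dose in Period 1 and the first LOXO-292 dose in Period 2".
- B1: 9 days (Days 1 to 9, SAP Table 5.1).
- B2: about 1 day (Day 10 to release on Day 11, SAP Section 3).
- Total to end of treatment: 1 + 9 + 1 = 11 days.

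**3. Share of time, and what it implies**

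Assumption, not in the documents: the onset of an event that cannot be placed is equally likely at any moment from first dose to end of treatment.

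- A: 1/11 = 9.1%
- B1: 9/11 = 81.8%
- B2: 1/11 = 9.1%
- After LOXO-292 has started: (9 + 1)/11 = 90.9%

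Under that assumption, about 91% of unplaceable events would be put in A although they began after LOXO-292 started. Follow-up days are left out. The call asks about events since the end-of-treatment or early-termination visit, and from that visit on only drug-related adverse events and serious adverse events are collected, so a constant rate does not suit that window.

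**4. Effect on a table cell**

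With 16 subjects dosed in a segment, one subject is 1/16 = 6.25 percentage points of a column. This is a maximum per row and per affected subject, because a subject counts once within a category. If the subject already has that event in the column, the cell does not change.

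**The case against.** The strongest reply is the exception clause. A reader who stops at the first half of the sentence might infer that every event with a missing date goes to repaglinide and never to LOXO-292. That is not what the SAP says: an undated event known to belong to Period 2 is outside the default. This stands and limits the point to events that cannot be placed at all.

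A reader might also argue that dates are most often lost for events recalled on the follow-up call. The documents do not support this as a route into Treatment A. The question put to subjects (Protocol 13.2.7.2) concerns the time since the last visit, so for subjects who reached end of treatment the event is known to fall after Period 2. What remains is a small gap in wording: such an event is arguably neither inside nor between treatment periods, so the SAP should say where it goes.

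It is also tempting to say that the missing-date rule contradicts the missing-time rules. It does not. They cover different cases and can all be applied, and counting under two treatments is only one of the two missing-time rules. The fair statement is that they differ in direction.

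Finally, the event is not lost. Relationship is recorded separately for each drug, all events are listed by subject, serious events get a table and narrative, and the Overall column is unchanged. Investigator judgment also enters attribution, although the SAP does not say that it overrides this default. Subjects are confined from Day -1 of Period 1 to end of treatment or early termination, so unplaceable onsets should be rare. All of this stands as a limit on importance. None of it gives a reason for choosing Treatment A alone.

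**Conclusion.** The point holds in a narrow form and is minor. For an adverse event with no onset date and no known period, the SAP's default is always the roughly 24-hour repaglinide segment. That default can understate B1 or B2 and cannot overstate them.

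The 91% figure rests wholly on the uniform-onset assumption and applies only to events that cannot be placed. It should not be read as the share of all events with a missing date that are misassigned. The 6.25-point figure assumes 16 subjects dosed and is a ceiling per affected subject. The documents give no expected number of such events, so the total effect cannot be estimated; confinement suggests that it is small. The Overall counts are unaffected.

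**What to change.** In SAP Section 7.3, keep the exception clause and change the default. An event whose onset date is missing and whose onset cannot be placed is counted as treatment-emergent under every treatment segment (A, B1, B2) that the available information cannot rule out. Add that an undated event known to have begun after end of treatment is attributed to the last treatment given. If the sponsor prefers the present default, the SAP should give the reason for it.

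The cost is a sentence or two in the SAP and a small programming change. The downside is that a rare event may be counted in more than one column. The section already accepts this for two treatments when the onset time is missing on a dosing date; counting across three segments extends that convention. A table footnote would make any such event visible.
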